4. GENERAL ISSUES FOR DATA ANALYSIS

4.1. General

Descriptive statistics for continuous variables will include the number of observed values, the mean, standard deviation (SD), median, minimum, and maximum values. Geometric mean (GM) and percent coefficient of variation (%CV) will also be used to describe continuous pharmacokinetic variables. For categorical variables, the number and percentage of subjects with a specific level of the variable will be presented.

Unless otherwise specified, all reported p-values will be assessed for statistical significance at the two-sided 0.05 level, and all confidence intervals (CIs) for individual group parameters will be computed at the 95% coverage level. Dilution (Part 1) and dose (Part 2) group comparisons will be made using 90% CIs for GM ratios, with no adjustment for multiple testing.

4.2. Specification of Baseline Values

The baseline values for any measurement is the last value obtained prior to injection of study drug, unless otherwise noted.

4.3. Handling Withdrawals and Missing Data

The primary pharmacodynamics outcome of time to ovulation, defined as a single elevated serum $P \ge 4.7$ ng/mL, will be censored at month 12 following treatment initiation. No imputation of event times prior to month 12 will take place for the primary analysis, although sensitivity analyses may consider outcomes as interval-censored between the dates of last P < 4.7 ng/mL and first $P \ge 4.7$ ng/mL. Missing MPA concentrations at key time points (eg, end-times of partial AUCs) will be imputed using methods specified in Section 14 of the SAP. Incomplete AE onset or CM initiation dates may be imputed to assess safety or when censoring participants from analyses due to excluded medication use, as follows:

- If a participant cannot recall the day or month of onset/initiation, then the date will be imputed as the last clinic visit without evidence of the AE or CM use, or other adjudicated date based on best clinical judgment.
- If a participant can only recall the month of onset/initiation, then the date will be imputed as the first day of the month or the last clinic visit prior to the AE/CM, whichever is later.

4.4. Study Days and Visits

The start of treatment (day 0) is defined as the date on which a subject receives a dose of study drug. The study day on which an event occurs or an outcome is assessed will be calculated as the date of the event or outcome, minus the date of treatment initiation; a negative study day indicates an event prior to study drug administration. When necessary and appropriate, fractions of study days will be computed based on the time (in hours and minutes) of a subject's injection and the time of her event or outcome assessment.

Some pharmacokinetic and pharmacodynamics data will be assigned to visit windows when reporting by-visit summaries (eg, serum concertation on day 182). In order to maximize the use of available data, the window periods used in these summary analyses may be wider than

specified in the study Manual of Procedures (MOP) (see Table 1, below). If multiple data fall in the same visit window, then the value closest to the nominal time will be used. If multiple data in the same visit window are equally distant to the nominal time, then the last value in the visit window will be used for the analysis.

Table 1: Windows used when summarizing Pharmacokinetic and Pharmacodynamics data by study visit

Target Visit	Window Period (MOP)	Window Period (Analysis)
Days 1, 2	± 1 hour	+/- 3 hours
Days 3, 5, 7	± 3 hours	+/- 6 hours
Days 10, 12, 14, 18	± 24 hours	+/- 24 hours
Days 21 and after	± 48 hours	+/- 84 hours

5. STUDY POPULATION

5.1. General

The study will enroll healthy women 18 to 40 years of age, inclusive, who are at low risk of pregnancy (eg, sterilized, in exclusively same-sex partnership, in monogamous relationship with vasectomized partner, or using a non-hormonal itrauterine device), and who are confirmed to have ovulated during the pre-treatment phase of the study.

5.2. Subject Disposition

The numbers of participants screened and enrolled in Part 1 and Part 2 of the study will be tabulated by investigational center and treatment group, and pooled across centers and groups. A flow diagram will be provided which presents the numbers and percentages of participants contributing to the Treated and Primary Evaluable Populations; reasons for exclusion from analysis populations; total women-years (WY) of follow-up contributed to each analysis set (by treatment group); and the numbers and percentages of participants who complete the study, discontinue early (overall and by reason), or who are lost to follow-up. Subjects that were excluded from the various analysis populations and reason for exclusions will be listed.

5.3. Demographics and Baseline Characteristics

Summary statistics appropriate to the measurement scale will be used to describe baseline demographic, behavioral, and contraceptive use history data. Continuous variables may also be described using categorical levels chosen based on previous experience with similar studies, and prior to un-blinding of statisticians. Baseline data will be presented for the Screened Population, the Treated Population, and the Primary Evaluable Population. Summaries will be provided by study Part (1 or 2), treatment group, investigational center, and pooled across centers and groups. No statistical testing will be performed to compare distributions of baseline characteristics between dilution or dose groups. However, baseline characteristics may be compared between investigational centers using exploratory analysis of variance for continuous variables or Chi-Squared tests for categorical variables in order to help interpret any apparent differences (or lack of differences) in pharmacodynamics and pharmacokinetic responses between centers.

5.4. Prior Therapy and Medication use

Start and stop dates of medication or non-drug therapy will be compared to the start date of study drug dosing to allow medications/treatments to be classified as either *prior* or *concomitant*. Prior medications include any previous therapy, medication, or procedure a subject has had within 30 days before study drug administration. Prior medication use will be documented, and the prevalence of use will be summarized by therapeutic class of medication and category (coded using Lexicomp and PDR Online).

5.5. Medical History

Pre-existing medical history data will be coded using the Medical Dictionary for Regulatory Activities (MedDRA) and summarized in tables and listings by system organ class (SOC), preferred term, and highest severity, both within treatment group and overall.

5.6. Physical Examinations

See Section 8.58 for description of vital signs, body weight, and other physical exams results to be presented in the CSR.

5.7. Childbearing Potential and Methods of Contraception

Information related to childbearing potential (including average menstrual cycle length, duration of menstrual bleeding, etc.) and contraceptive method use during the study will be collected at baseline and summarized using descriptive statistics.

5.8. Study Protocol Violations

Data from subjects with any protocol violations (as recorded on protocol violation case report forms [CRFs]) during the study will be summarized in frequency tables. Categories of deviations will include violations of study entry criteria (eg, use of excluded medications), randomization errors, violation of study withdraw criteria and other violations captured on CRFs. All protocol violations will be further summarized in data listings.

6. EFFICACY ANALYSIS

Efficacy will not be evaluated in this study.

7. MULTIPLE COMPARISONS AND MULTIPLICITY

No adjustments will be made for the planned or unplanned multiple comparisons of primary or secondary pharmacokinetic or pharmacodynamic endpoints.

8. SAFETY ANALYSIS

8.1. General

Safety analyses will be performed on the Treated Population. Results of all safety assessments, including AEs, ISRs, delayed return to ovulation, menstrual bleeding pattern change, vital sign and body weight, and use of CMs will be summarized with descriptive statistics by treatment group and overall, and/or presented in data listings.

8.2. Adverse Events

All AEs will be coded using MedDRA by preferred term and SOC. The number and percentage of participants experiencing AEs will be presented by treatment group: overall, by severity, relatedness to treatment, and according to whether or not the event had an onset date within 7.5 months of initiation of treatment. Serious adverse events and adverse events leading to withdrawal from the study will be summarized separately.

A listing of all AEs will include treatment group, verbatim AE description, preferred term and SOC, duration, relatedness to product, seriousness, severity, outcome, and whether withdrawal from the study occurred as a result of the AE. All relevant information on any deaths will be discussed in the subject narrative included in the clinical study report.

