### 3.14.3.2. Follow-up (Day 1 to Week 78)

Regardless of ovulation status, all subjects should remain in follow-up for at least 52 weeks postinjection.

There are 2 types of follow-up visits in this study: scheduled follow-up visits and laboratory visits.

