### 3.14.4. Procedures After Study Drug Treatment and Lost to Follow-up

## 3.14.4.1. Final Visit

Subjects will complete the study at 12 months after administration of TV-46046, or after ovulation returns (if after month 12) or at the week 78 laboratory visit (if ovulation does not return before then). If Part 2 is not initiated, subjects in Part 1 may be discontinued from the study as early as 26 weeks following study drug injection. If Part 2 is initiated, subjects will stay in the study for a minimum of 12 months (52 weeks) from start of TV-46046 treatment even if ovulation returns before then. All subjects will complete the study by 18 months (78 weeks) from the start of TV-46046 treatment even if ovulation does not return by then. Additional post-discontinuation follow-up may be considered for safety purposes until ovulation returns and/or MPA levels become undetectable.

For subjects in whom ovulation returns before month 12 post-injection, the final study visit will be scheduled at month 12. If ovulation occurs between months 12 and 18 (between weeks 52 and 78), at the time when the defining serum progesterone result becomes available, the study staff will inform the subject that she needs to return within 5 days to the investigational center for the final study visit. For subjects in whom ovulation does not return by month 18, the laboratory visit at week 78 will be considered the final study visit.

The following procedures/assessments will be performed during the final visit:

- obtain blood sample for serum MPA (approximately 5 mL)
- obtain blood sample for serum progesterone, estradiol (approximately 10 mL), if indicated; and liver function tests (Part 2 only, approximately 5 mL)
- measure body weight
- measure vital signs (BP [systolic/diastolic], pulse, and respiration)
- perform breast exam
- interview about acceptability
- evaluate site of injection for ISRs
- inquire about adverse events
- inquire about concomitant medications
- interviews about mood (Part 2 only) and menstrual bleeding pattern

If the subject cannot return to the investigational center in person, the final evaluation may be completed by telephone (to the extent possible) and documented in the CRF.

For subjects who withdraw prematurely from the study, the final visit will be performed at the time of discontinuation, if known.

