## 7.1.2. Recording and Reporting Adverse Events

For adverse event recording, the study period is defined for each subject as that time period from signature of the informed consent form to the end of the follow-up period.

All adverse events that occur during the defined study period must be recorded on the source documentation and transcribed onto the CRF, regardless of the severity of the event or judged relationship to the study drug. For serious adverse events, the Serious Adverse Event Form must also be completed and the serious adverse event must be reported immediately (see Section 7.1.5.3.1). The investigator does not need to actively monitor subjects for adverse events once the study has ended. Serious adverse events occurring to a subject after study discontinuation should be reported to the sponsor if the investigator becomes aware of them, following the procedures described in Section 7.1.5.3.1.

At each of the 3 scheduled follow-up visits, the investigator or designee must question the subject about adverse events by asking an open-ended question such as, "Have you had any unusual symptoms or medical problems since the last visit? If yes, please describe." All reported or observed signs and symptoms will be recorded individually, except when considered manifestations of a medical condition or disease state. A precise diagnosis will be recorded whenever possible. When such a diagnosis is made, all related signs, symptoms, and any test findings will be recorded collectively as a single diagnosis on the CRF and, if it is a serious adverse event, on the Serious Adverse Event Form. During frequent laboratory visits adverse events will not be actively solicited but will be documented if reported by the subject.

The clinical course of each adverse event will be monitored at suitable intervals until resolved or stabilized or returned to baseline, or until the subject is referred for continued care to a another healthcare professional, or until a determination of a cause unrelated to the study drug or study procedure is made.

The onset and end dates, duration (in case of adverse event duration of less than 24 hours), action taken regarding study drug, treatment administered, and outcome for each adverse event must be recorded on the source documentation and transcribed onto the CRF.

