8.5. Menstrual Bleeding Disturbances

The percentage of women experiencing amenorrhea or other menstrual bleeding disturbances (irregular bleeding or spotting) assessed monthly and at day 7, week 13, week 32, and the final study visit will be compared between treatment groups using frequency tables (for monthly data, the bleeding history report obtained closest in time to the target monthly visit - among visits within 14 days of the target - will be used). The number and percentage of subjects ever reporting spotting, irregular bleeding, or unacceptable bleeding pattern will also be tabulated.

For Part 2 only, weekly diary data were divided into 30-day segments starting from the date of the injection. For each 30-day period, subjects were categorized into one of the following four types:

- No bleeding or spotting: no bleeding or spotting days recorded during the entire 30-day period.
- Spotting only: only days with spotting recorded during the 30-day period
- 3. Bleeding only: only days with bleeding recorded during the 30-day period

 Bleeding and spotting: a mixture of bleeding and spotting days recorded during the 30day period.

The percentage of subjects experiencing each of the four bleeding patterns during months 1, 3, 6, 9, and 12 will be compared between treatment groups using frequency tables.

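### By-cohort adverse-event percentages overall and after 7.5 months pool follow-up that lasts longer when ovulation is delayed, so a difference in the late row may partly reflect observation time

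*SAP*

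**What the plan says.** **How AEs are tabulated.** SAP 8.2 (Adverse Events) plans: "The number and percentage of participants experiencing AEs will be presented by treatment group". One breakdown is "according to whether or not the event had an onset date within 7.5 months of initiation of treatment". The earlier stratum is bounded at 7.5 months (week 32 in the protocol's visit schedule). The later stratum has no stated end.

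**How long AEs are recorded.** Protocol 7.1.2 defines each woman's recording period as running "from signature of the informed consent form to the end of the follow-up period", so it closes with her own follow-up.

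**How long follow-up lasts.** Protocol 3.14.3.2 says "all subjects should remain in follow-up for at least 52 weeks postinjection". Protocol 3.14.3.2.3 adds visits at weeks 61 to 65 for women with no ovulation by week 52, and at weeks 74 to 78 if ovulation has still not returned by week 65. Protocol 3.14.4.1 sets the ceiling: "All subjects will complete the study by 18 months (78 weeks) from the start of TV-46046 treatment". The same section, with Protocol 3.11, allows Part 1 women to leave from about 26 weeks after injection if Part 2 is not started. The SAP (footnote 1 and section 13.3) records that Part 2 never ran.

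**Related items.** SAP 5.2 reports "total women-years (WY) of follow-up contributed to each analysis set" by treatment group, but only as part of subject disposition. SAP 8.5 adds a count of women "ever reporting spotting, irregular bleeding, or unacceptable bleeding pattern will also be tabulated", again with no end date. Elsewhere the SAP does deal with time after month 12: it censors time to ovulation at month 12 (4.3, 11.2) and describes later pharmacokinetic data separately (10). SAP 8.2 has no matching rule.

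**The concern.** Length of follow-up past week 52 is decided by whether ovulation has returned, and delayed ovulation is an effect of the drug. A crude percentage of women with at least one AE rises with time observed. If the cohorts differ in how many women are still anovulatory at week 52, the overall and late rows mix AE risk with observation time. The cohorts could differ in this way: Protocol 3.2 gives injection volume as a possible influence on release rate, which is why Part 1 tests more than one concentration.

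Comparing safety across concentrations is a secondary objective. With cohorts of 6, one woman is 16.7 percentage points, so a reader may make much of a one- or two-woman difference in the late row.

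**Working it through.** The documents give no AE rate and no figure for this effect, so there is nothing of the plan's own to reproduce. The check uses the protocol's weeks and an assumed rate.

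**Inputs**
- Start of the late row: week 32 (SAP 8.2, with month 7.5 equated to week 32 in Protocol 3.1).
- Usual end of follow-up: week 52 (Protocol 3.14.3.2). Latest end: week 78 (Protocol 3.14.4.1).
- Cohort size: 6 (SAP 2.1).
- AE rate *r* per woman-year: **assumed** constant. Range 0.5 to 2, central value 1.

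**Step 1: exposure per woman**
- Overall: 78/52 = 1.5.
- Late row: (78 − 32)/(52 − 32) = 46/20 = 2.3. This is the maximum. A woman found to have ovulated at week 61 has about 61 − 32 = 29 late weeks, a ratio of 29/20 = 1.45.

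**Step 2: chance of at least one late AE per woman**, 1 − exp(−*r* × weeks/52)
- *r* = 1: 1 − exp(−20/52) = 31.9%; 1 − exp(−46/52) = 58.7%.
- *r* = 0.5: 17.5% and 35.7%.
- *r* = 2: 53.7% and 83.0%.

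**Step 3: expected late-AE percentage for a cohort of 6** with *k* women followed to week 78, [(6 − *k*) × p20 + *k* × p46]/6

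| *k* of 6 to week 78 | *r* = 0.5 | *r* = 1 | *r* = 2 |
|---|---|---|---|
| 0 | 17.5% | 31.9% | 53.7% |
| 1 | 20.5% | 36.4% | 58.5% |
| 3 | 26.6% | 45.3% | 68.3% |
| 6 | 35.7% | 58.7% | 83.0% |

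For *k* = 1 and *r* = 1: (5 × 0.319 + 0.587)/6 = 0.364. That is 4.5 points, or 0.27 of a woman, above *k* = 0.

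**Step 4: overall row.** If p52 is the percentage with any AE by week 52, the constant-rate value at week 78 is 1 − (1 − p52)^1.5. For p52 of 20%, 50% and 90% this gives 28.4%, 64.6% and 96.8%. With all 6 extended, the excess over p52 values from 20% to 90% is about 7 to 15 points, under one woman in 6. With one extended it is 1.1 to 2.4 points.

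**Step 5: how many women might be extended.** The only related figure in the documents is for an approved subcutaneous product after multiple doses: 12 of 15 women (80%) ovulated within a year of the last injection (Protocol 1.4.2). Taking 20% not ovulated, purely as illustration, the chance that at least one of 6 is extended is 1 − 0.8^6 = 0.74. At *r* = 1 the expected late-row excess is 0.2 × (58.7 − 31.9) = 5.4 points if every such woman stays to week 78.

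**Step 6: effect of the remedy.** If the late row stops at week 52, each woman who stays to week 52 contributes 20 weeks, so at *r* = 1 the expected value is 31.9% whatever *k* is. Per woman-year, expected events over exposure are (20/52)/(20/52) = 1 and (46/52)/(46/52) = 1, so the rate does not depend on length of follow-up.

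**The case against.** The strongest case on the other side is that the plan already shows most of what a reader needs, and that the effect is modest. The 7.5-month split is pre-specified. Women-years by group, Kaplan-Meier estimates of delayed ovulation (SAP 8.4) and a listing of all AEs are planned. Safety summaries are descriptive, Part 1 is unpowered and its cohorts are sequential, so no error rate is affected. All of this stands, and it limits the importance of the point. It does not supply a comparable late row: the women-years are not linked to the AE tables, and the items named for the AE listing in SAP 8.2 include duration but not onset date or study day.

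Ascertainment is a second fair objection. Laboratory visits record AEs only if volunteered (Protocol Table 1, footnote j), so after week 32 every completer has one solicited inquiry, at the final visit. This may shrink the imbalance below the constant-rate figures. It need not remove it, because that inquiry looks back over 20 weeks for some women and up to 46 for others.

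Four stronger readings are tempting, and the documents do not support them:
- *A longer-acting cohort will look less safe.* This needs the cohorts to differ in delayed ovulation. All Part 1 cohorts receive 120 mg, and no such difference is given.
- *32% versus 59% is the expected cohort gap.* It contrasts two individual women, or a cohort with nobody extended against one with all 6 followed to week 78.
- *The within-7.5-month row has equal follow-up.* The permitted exit from week 26 falls before week 32, so this holds only if nobody leaves early.
- *The bleeding count is equally affected.* SAP 13.3 calls it exploratory, time-specific bleeding tables accompany it, and Protocol 1.4.2 says most users of the approved products have disrupted bleeding, so it is probably near its ceiling before week 52.

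**Conclusion.** The point holds as a minor reporting gap. The overall and late AE percentages in SAP 8.2 cover unequal observation time that depends partly on the drug's effect, and nothing in that section adjusts for it. The possible distortion is towards more AEs in a cohort with more delayed ovulation, and it is concentrated in the late row. Under a constant rate of 1 AE per woman-year, the excess is about 4.5 points with one of 6 women extended to week 78 and about 13 points with three (45.3 − 31.9 = 13.4). It reaches 27 points only if all 6 are extended.

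These sizes rest on an assumed rate, constant ascertainment and the maximum extension, so they are better read as upper values at each assumed rate. No decision rule or test depends on them.

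Two qualifications apply. First, the 52-week minimum in Protocol 3.14.3.2 and the 26-week exit in Protocol 3.11 and 3.14.4.1 need to be reconciled. If early exits occurred, follow-up would range up to 78/26 = 3.0-fold and would be unequal even before week 32. Second, a reader might infer that the overall AE table should stop at week 52. The documents do not support that: follow-up beyond week 52 exists for safety reasons in a first-in-human study (Protocol 3.1), and those events belong in the full count.

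**What to change.** Keep the full overall AE table in SAP 8.2 and add:

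1. By-cohort rows for AEs with onset up to week 52, and for onset after 7.5 months up to week 52.
2. A separate report of AEs with onset after week 52, with the number of women still followed in each cohort.
3. AEs per woman-year by cohort, overall and after 7.5 months. The late denominator comes from injection and follow-up dates already collected. These rates also allow for early exits, which a week-52 cut alone does not, provided the AE rate is roughly constant.
4. Optionally, the exploratory bleeding count in SAP 8.5 to week 52 as well.

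The cost is SAP wording and a few table rows. No new data are needed, because Protocol 7.1.2 already requires AE onset dates and SAP 5.2 already plans women-years. The drawback is that woman-year rates from 6 women per cohort will be imprecise, and a constant rate may not suit a depot whose concentrations decline. They should be presented as descriptive companions to the counts.
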